16.1.5. Subgroup Analyses of Adverse Events

Subgroup analyses of patient incidence and EAIR of TEAE for age group (<65, 65-75, ≥ 75 years), sex, and race (white vs non-white), baseline eGFR category (<60, 60-90, ≥90 mL/min/1.73m²), baseline glycemic status (normoglycemic, prediabetes, and diabetes), baseline ezetimibe use (yes/no) will be presented by SOC and PT in descending order frequency.

16.2. Death and Major Adverse Cardiac Events

For this study deaths and positively adjudicated MACE (MI, stroke, coronary revascularization, hospitalization for unstable angina) are study endpoints and per protocol are not recorded in the Adverse Event CRF. They will be reported as adjudicated endpoints in listing and tables using the FAS.

In addition, all events leading to death as reported by the Investigator will be summarized by SOC/PT and treatment group using the SAS, and for patients in the SAS with baseline ezetimibe use.

16.3. Safety Laboratory Evaluations

The list of central laboratory assessments to be included in the outputs is included in the Table 4 of the Protocol (Section 12.1.6.1) and includes H_bA_{1c}. Urinalysis is not quantitative, and coagulation is measured at selected patients/visits only, and these will not be summarized.

In addition, eGFR will be calculated using the formula: $186 \times (\text{creatinine}/88.4)^{-1.154} \times (\text{age})^{-0.203} \times (0.742 \text{ if female}) \times (1.210 \text{ if Black})$, where creatinine is in μmol/L. Blood urea nitrogen (BUN)/creatinine ratio (BUN/Creatinine ratio) will also be calculated.

Summaries for all lab results will be included for the below analyses:

- Observed and change/percent change from baseline by analysis visit for hematology and blood chemistry measurements.
- Creatinine and eGFR will be summarized by treatment group and by baseline eGFR categories (<30, 30 to <60, 60 to <90, and ≥90 mL/min/1.73m²).
- Fasting glucose and HbA_{1c} will be summarized by baseline glycemic status, and by treatment group.

[figure not shown]
The analyses for shift tables from baseline to the worst post-baseline category or value are presented in Table 2. Note that for fasting glucose and HbA_{1c} the analyses will be by baseline glycemic status.

Table 2: Analyses for Shift Tables of Laboratory Parameters

Parameter	Categories (From Better to Worse)
Fasting glucose (by baseline glycemic status)	<51 mg/dL ≥51 to <100 mg/dL ≥100 to <126 mg/dL ≥126 mg/dL
H _b A _{1c} (by baseline glycemic status)	<5.7% ≥5.7% and <6.5% ≥6.5 to <7% ≥7%
Alanine aminotransferase (ALT)	Normal, High (> ULN)
Aspartate aminotransferase (AST)	Normal, High (> ULN)
eGFR	≥90 mL/min/1.73m ² ≥60 to <90 mL/min/1.73m ² ≥30 to <60 mL/min/1.73m ² <30 mL/min/1.73m ²
Uric acid (UA)	Low/Normal (combined) High (> 5.7 mg/dL for female, >7.0 mg/dL for male)

Lab abnormalities associated with AESIs are listed in Appendix 7 and will be summarized with the AESIs. In addition, for evaluation of potential Hy’s Law cases, a pairwise scatterplot will be created with the maximum (peak) post-baseline values of ALT or AST as multiples of the ULN, against the concomitant TB (also multiples of the ULN).

Other lab abnormalities of selected parameters are presented in Table 3 and the number of patients meeting each criterion will be summarized by treatment group.

Patients with potentially clinically significant laboratory abnormalities (Appendix 10) will be listed. For a given parameter (or group of parameters as indicated), all values from the patient will be included in the listing if any value meets the criteria.

As a result of the pandemic, local laboratory may be used for safety labs at the investigators’ discretion. The local lab data are reviewed and evaluated by the investigators for any abnormalities and adverse event reporting as applicable. Due to the diverse use of units and

variation in laboratory normal ranges, the local lab data are not used in the statistical analyses. All local laboratory measurements will be listed with the associated reference ranges if available. Abnormal laboratory results of ALT and/or AST $>3 \times$ ULN, TB $>2 \times$ ULN or CK $>5 \times$ ULN based on the non-central laboratory reference ranges (when available) will be noted in the listing.

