4.2.2. Nonclinical Experience

The primary pharmacology of bempedoic acid was evaluated in several well-characterized and predictive rodent models of dyslipidemia. In these studies, bempedoic acid lowered LDL-C and triglycerides (TGs) and increased high-density lipoprotein cholesterol (HDL-C). In a study of cholesterol-fed LDL receptor-deficient mice, bempedoic acid substantially slowed the progression of atherosclerosis in a dose-related manner.

Results of the nonclinical safety pharmacology studies did not identify any significant risks for subjects over the mean range of bempedoic acid exposures in clinical studies.

In toxicology studies, evaluations of bempedoic acid in mice, rats, and monkeys in oral studies up to 52 weeks in duration have been completed. No significant central nervous system (CNS),

respiratory, or CV liabilities were identified. Target organs identified in repeat-dose studies were liver in rats, and liver and kidney in monkeys, and changes were reversible following cessation of treatment. Changes in clinical laboratory parameters indicative of hepatic and renal function were observed in animals at doses lower than those associated with frank toxicity.

Bempedoic acid is nonmutagenic and nonclastogenic in both in vitro and in vivo genetic toxicology assays.

In the pivotal 26-week rat study, the no-observed-adverse-effect level (NOAEL) dose was 30 mg/kg/day in rats and the corresponding area under the curve during 24 hours (AUC_{0-24}) values of the sum of bempedoic acid and its metabolite ESP15228 were up to 528 $\mu\text{g}\cdot\text{hr}/\text{mL}$. In the pivotal 52-week monkey study, the NOAEL dose was 60 mg/kg/day and the corresponding AUC_{0-24} values of the sum of bempedoic acid and ESP15228 were up to 4760 $\mu\text{g}\cdot\text{hr}/\text{mL}$.

In vitro studies indicated that bempedoic acid is neither an inhibitor nor inducer of major cytochrome P450 (CYP) enzymes at clinically relevant plasma concentrations. In addition, bempedoic acid does not appear to inhibit major drug transporters.

Please refer to the most recent Investigator's Brochure (IB) for additional information regarding pharmacology, pharmacokinetics (PK), and nonclinical safety studies.

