15. STATISTICS

15.1. General Considerations

The statistical analyses described in this section will be performed as further outlined in a separate Statistical Analysis Plan (SAP), which will be finalized prior to the first time that the DMC reviews data for this study. The SAP will supersede the protocol in the event of any differences between the 2 documents in the plans for data analysis, and the protocol will be amended if appropriate. The SAP will be included as an appendix in the clinical study report for this protocol.

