15.8. Safety Endpoints

General safety data in this study includes AEs, clinical safety laboratories, PEs, vital signs, and ECGs. The summarization of AEs will include only TEAEs, defined as AEs that begin or worsen after randomization and ingestion of the first dose of IMP. TEAEs and SAEs will be summarized by System Organ Class (SOC), severity, and relationship to IMP for each treatment group.

AE summaries will be provided overall and for subgroups such as gender and age. Deaths, withdrawal from study treatment due to AEs, and withdrawal from the study due to AEs will each be summarized by treatment group.

Clinical safety laboratories, including hematology, blood chemistry, and urinalysis; PE findings; vital signs; ECG readings; and weight will be summarized by the value and by change from baseline in the value (where appropriate) at each postbaseline time point.

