15.8.1. Adverse Events of Special Interest (AESI)

All AESI will be identified and evaluated by routine safety monitoring of AEs and laboratory values (where appropriate) and will be summarized by severity and relationship to IMP for each treatment group.

The following are considered AESI categories for this study:

- Hepatic Safety, including liver-associated enzymes, TB, and any Hy's law cases ($\geq 3 \times$ ULN for either ALT or AST, with accompanying TB $>2 \times$ ULN in the setting of no known other cause)
- Musculoskeletal Safety, including CK
- Diabetes and Glycemia, including new onset of diabetes and worsening of diabetes
- Hypoglycemia Associated with Metabolic Acidosis
- Renal Impairment, including lab measures of renal function
- Neurocognitive Events
- Atrial Fibrillation
- Tendon Rupture/Tendinopathy. The TRAC will adjudicate events of tendon rupture per the TRIAC, and adjudicated events will be summarized.
- Malignancies

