⁵ Pregnancy test completed in premenopausal women only, serum test at Week -5 (Visit S1) and urine test at Day 1 (Visit T1); FSH completed on postmenopausal women <55 years of age.

⁶ Clinical safety laboratory tests include hematology, blood chemistry, and urinalysis. Urinalysis includes dipstick measured at the clinic and microscopic, if abnormal, completed by the central lab. A limited safety laboratory assessment (ALT, AST, TB, and CK) will be completed at Visit T2 only. A coagulation panel will be completed only if needed for patients on anticoagulant therapy at Day 1 (Visit T1) and 3 to 5 days later.

⁷ Basic fasting lipids include TC, calculated LDL-C, HDL-C, non-HDL-C, and TGs.

⁸ After Visit T4 (Month 6), telephone and clinic visits (alternating every 3 months) will continue until the study is completed.

⁹ All procedures will be completed at the End of Study or Early Termination Visit.

¹⁰ Duration of treatment for each patient will vary and is dependent on accumulation of MACE in the entire study. For individual subjects, treatment duration will be a minimum of 24 months and may continue for up to approximately 57.5 months.

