8.6. General Principles

Descriptive statistics (n, mean, standard deviation, median, 1st quartile, 3rd quartile, minimum, and maximum) will be calculated for continuous data as appropriate.

Categorical data will be summarized using counts and percentages. Missing values may be presented as a separate category when appropriate. Counts of zero in any category will be presented without percentage. Ninety-five percent (95%) confidence intervals (CIs) of the means or percentages may be calculated for selected continuous and categorical variables.

For time-to-event endpoints, Kaplan-Meier (KM) curves will be presented graphically by treatment group. KM estimates of cumulative incidence rates at specified time intervals (e.g., month 6, year 1, year 2, and yearly after randomization) and their 95% CIs will be presented. The hazard ratio and its corresponding 95% CI will be estimated from a Cox proportional hazard (PH) model with treatment group in the model. For between-group comparison, p-values (2-sided) will be calculated using log-rank tests.

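### SAP 16.3 leaves urinalysis out of the laboratory summaries because it is not numeric, although Protocol 15.8 says it will be summarized and the SAP's own methods can handle categories

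*SAP*

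**What the plan says.** **SAP 16.3** takes Protocol Table 4 as the list of central laboratory assessments to be output, then makes an exception: "Urinalysis is not quantitative, and coagulation is measured at selected patients/visits only, and these will not be summarized". The reason for urinalysis is the type of result. The reason for coagulation, selective measurement, is a separate matter and is not disputed here.

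**Protocol 15.8** says: "Clinical safety laboratories, including hematology, blood chemistry, and urinalysis; PE findings; vital signs; ECG readings; and weight will be summarized by the value", and also by change from baseline where that is appropriate, at each post-baseline time point. The synopsis says the same.

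**What is collected.** Protocol Table 4 includes protein and occult blood in the dipstick panel. The footnotes to Protocol Appendix 1 add: "Urinalysis includes dipstick measured at the clinic and microscopic, if abnormal, completed by the central lab".

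**Renal context.** Protocol 15.8.1 lists as an AESI category "Renal Impairment, including lab measures of renal function". Protocol 4.2.2 reports: "Target organs identified in repeat-dose studies were liver in rats, and liver and kidney in monkeys, and changes were reversible following cessation of treatment".

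**Precedence.** Protocol 15.1: "The SAP will supersede the protocol in the event of any differences between the 2 documents in the plans for data analysis". It adds that the Protocol will be amended if appropriate.

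**The concern.** The Protocol commits to a safety summary and the SAP withdraws it, on the ground that the results are not numeric. That is a reason for not reporting means and mean changes. It is not a reason for reporting nothing.

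What is at stake is one part of renal safety. The renal laboratory measures visible in the SAP are creatinine, eGFR, BUN and the BUN/creatinine ratio. These describe filtration. They do not record protein or blood in the urine. A modest excess of new dipstick protein in one arm, with eGFR unchanged, would therefore not show in the visible laboratory tables.

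**Working it through.** The plan states no figure on this point, so the check is a comparison of texts, with one count.

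**1. Is there a difference between the documents?** Yes. Protocol 15.8 and the synopsis name urinalysis among the laboratories to be summarized; SAP 16.3 says it will not be. Under Protocol 15.1 the SAP rule is the operative one.

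**2. Does the stated reason hold under the SAP's own rules?** Three places say no.
- SAP 8.6: "Categorical data will be summarized using counts and percentages".
- SAP 16.3, Table 2, is a set of shifts from baseline to the worst post-baseline category. It includes two-category rows for ALT, AST and uric acid.
- SAP 16.4 summarizes a three-category investigator rating of the ECG, which is not quantitative either.

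**3. Is the result shown by arm anywhere else in the visible text?**
- Table 2 has no urinalysis row.
- Appendix 10 (potentially clinically significant abnormalities, listed by patient) has no urinalysis criterion. Its catch-all row covers only chemistry and hematology.
- The body of Table 3 and Appendix 7, which holds the AESI laboratory criteria, are not in the available text, so their content is unknown. If either includes a urinalysis item, it conflicts with the exclusion sentence in SAP 16.3, which would still need correction.
- Adverse event tables: Protocol 13.1.3 asks for clinically significant laboratory abnormalities to be reported as AEs, and SAP 16 and 16.1.1 tabulate TEAEs by preferred term and arm. Protocol 13.2.3 limits this route. An abnormal value not already tied to an AE is recorded only if it leads to action on study drug, needs intervention, or is judged clinically significant by the investigator.

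**4. How much scheduled data is involved?** Protocol 10.6 and Appendix 1 schedule urinalysis at S1, T1, Month 3, Month 6, Month 12, every 6 months after that, and EOS. Month 1 has a limited chemistry panel only.
- Follow-up of 42 months (the Protocol's estimate of typical duration): Months 3, 6, 12, 18, 24, 30, 36 and EOS = 8 post-baseline dipsticks.
- Follow-up of 24 months (the planned minimum): Months 3, 6, 12, 18 and EOS = 5.
- Ceiling at 42 months: 8 × 14,000 = 112,000 scheduled results.

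This is an upper figure, because it ignores deaths, withdrawals and missed visits. Protocol 10.6.6, 10.6.8 and 10.6.9 also allow remote visits during COVID-19, and the minimum data set for those includes no laboratory samples.

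**The case against.** The strongest reply has four parts.

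- **The departure is open and governed.** The SAP states the change and gives a reason, and Protocol 15.1 lets it prevail. This stands as far as it goes: there is no unresolved contradiction over which rule applies. But precedence puts the omission into effect without justifying it, and Protocol 15.8 has not been brought into line.

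- **Renal safety is otherwise covered.** The SAP summarizes creatinine and eGFR by arm and baseline eGFR category, gives an eGFR shift table and calculates the BUN/creatinine ratio. TEAEs are tabulated by arm, with exposure-adjusted rates and a breakdown by baseline eGFR. A reader might infer from SAP 16.3 that proteinuria and hematuria are never shown by arm, but the documents do not support that: events reported as TEAEs are shown, and Table 3 and Appendix 7 cannot be read. What is missing from the visible text is the systematic view that does not depend on investigator judgment.

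- **The nonclinical signal is limited.** Kidney was a target organ in monkeys and not in rats, and the changes reversed. Protocol 4.2.2 mentions no urinary protein or blood. A reader might infer that a urinary effect in patients is expected; the text does not say so. This stands, and it keeps the point modest.

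- **The data may be noisy.** Dipsticks are read at the clinic, at up to about 1200 sites, and Table 4 gives no grading scale. SAP 16.3 keeps local laboratory data out of the analyses because units and ranges vary. This is a better argument than the one the SAP gives, and it should shape the table. It does not justify having none, since a normal/abnormal split needs no uniform grades.

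**Conclusion.** The point holds in a limited form. SAP 16.3 drops a summary that Protocol 15.8 and the synopsis promise, for a reason that SAP 8.6, SAP 16.4 and the SAP's own Table 2 contradict. In the visible text, dipstick protein and occult blood are not systematically tabulated by arm. Up to 8 scheduled post-baseline results per patient at 42 months are affected. No primary or key secondary analysis is touched.

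The conclusion assumes that Table 3 and Appendix 7 follow the exclusion sentence, and that dipstick results are held in the database in some categorical form. The documents confirm neither.

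A reader might go further and infer that the trial forgoes a powered test for a urinary effect, or could say nothing about one. Neither follows. SAP 16 plans no statistical comparison of safety data unless otherwise specified, and the documents give no background incidence from which power could be worked out. The results are still collected, and SAP 5.3 permits labelled ad hoc analyses. What is lost is a prespecified descriptive table.

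**What to change.** 1. In SAP 16.3, delete urinalysis from the sentence on assessments that will not be summarized.
2. Add to Table 2 a descriptive shift from baseline to worst post-baseline result for dipstick protein and for occult blood, by treatment group, in the safety analysis set. Use the result categories actually recorded, or normal/abnormal if grades are not uniform across sites.
3. If the sponsor prefers to keep the exclusion, state a reason that applies to categorical data and align Protocol 15.8 and the synopsis with it.

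Stratifying by baseline eGFR is optional.

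The cost is one edited sentence and two extra tables. No visit, sample or procedure is added. The downside is some noise from clinic-read dipsticks and from visits missed or held remotely during COVID-19; a footnote giving the number of patients with at least one post-baseline result in each arm would make that visible.

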6.3. Estimated Study Duration and Period

The estimated enrollment period is approximately 33 months. It is estimated the median treatment duration will be approximately 42 months (3.5 years), with all patients remaining in the study for a minimum of 24 months (2 years) and some patients remaining in the study for up to approximately up to 72 months (6 years). The study will continue until all 3 criteria for study end described in Section 6.5 have been met. Depending on the rates of accumulating endpoints in this study, the study duration may be shorter or longer. The estimated overall duration of the study (first patient first visit to last patient last visit) is approximately 72 months (6 years).

For each patient, the actual duration of treatment will depend on time of randomization versus when the 'End of Study' conditions have been met. All patients will be followed from randomization through the date of study termination unless the patient has withdrawn consent, irrespective of whether the patient is continuing to receive study treatment.

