10.6. Procedures and Schedule of Assessments

The study is comprised of 3 distinct periods: screening, run-in, and double-blind treatment.

The schedule of study events is provided in Appendix 1. However, a patient can be seen at any time for reasons of safety.

Note: If the patient discontinues IMP at any time after T1, please proceed to Section 10.7 for detailed instructions.

- If the patient agrees to clinical visits after withdrawing from IMP at any time after Visit T1, the visit will include all procedures and assessments except for those pertaining to IMP management (IMP dispensing, adherence, and accountability).
- If the patient agrees to telephone or other form of contact after withdrawing from IMP at any time after Visit T1, the contact will include collection of patient-reported information to complete the eCRF including concomitant medication use, AEs, SAEs, and potential clinical endpoints.
- Patient is expected to continue to receive IMP and complete study visits following a clinical endpoint unless, for some reason, this is no longer clinically appropriate.

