6.3. Safety Analysis Set [SAS]

The safety analysis set (SAS), used for all the safety summaries, is defined as all patients in FAS who received at least 1 dose of double-blind IMP. Patients in the SAS will be grouped according to the *actual* treatment received, in particular:

- patients who were randomized to bempedoic acid but received placebo only will be included in the placebo group;
- patients who were randomized to placebo but received at least one dose of study IMP bempedoic acid will be included in the bempedoic acid group. Note that this does not apply to patients who received commercial bempedoic acid or commercial fixed dose combination of bempedoic acid and ezetimibe.

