7.2.4. Analysis Visit Windows

For data analysis purpose, unless otherwise specified, study assessments will be assigned to analysis visits based on the Study Day (Section 7.2.2), and analysis visit windows specified in Appendix 3.

For lipids parameters (LDL-C, non-HDL-C, TC, HDL-C, TG) and hs-CRP, the *date of randomization* will be used as the start date to determine the analysis visit windows. For hs-CRP only, the end-of-study (EOS) measurement is defined as the last measurement taken for the patient.

In cases where multiple assessments fall into the same analysis visit, and only one is used for analysis, it is selected based on the following rules.

- The assessment closest to the target (nominal visit) date will be used.
- If there are ties, the assessment after the target date will be used.
- If multiple values are available with the same date and time, the assessment with larger laboratory accession number (LBREFID) will be used.

Note that unscheduled visits are treated the same way as scheduled visits.

Nominal visits (e.g., S1, S2, T1, etc, see Appendix 1) may be used in listings as appropriate.

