15.4.2. On-Treatment Analysis

An on-treatment analysis will also be conducted for primary time to 4-component MACE (MACE-4) and 3-component MACE (MACE-3) endpoints in the PPS.

The sensitivity analyses will also be performed for the time to first occurrence of NODM on treatment for patients with baseline glycemic status of no diabetes, prediabetes, or normoglycemic in the PPS.

For these on-treatment analysis, events (MACE-4, MACE-3 or NODM) that occurred after DLDOSE + 30 days will be ignored. Patients who did not have events before that will be censored at the earlier of the DLDOSE + 30 days and DLASMT, the date of censoring for non-fatal events defined in Section 7.2.5.

[figure not shown]
On-treatment analyses will be performed for lipid parameters and biomarkers including LDL-C, HDL-C, non-HDL-C, total cholesterol, triglyceride, hs-CRP, HbA_{1C} and fasting glucose. For these endpoints, values measured more than 7 days after the Date of Last Dose of IMP will be excluded, and only observed values prior to that will be summarized by treatment groups, and for HbA_{1C} and fasting glucose also by baseline glycemic status.

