16. SAFETY OUTCOMES

The Safety Analysis Set (SAS) will be used for all safety analyses. All adverse event tables will be summarized by treatment group. There will be no statistical comparisons between the treatment groups for safety data, unless otherwise specified.

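### Later by-visit laboratory means in SAP 16.3 mix on-drug and off-drug values, which dilutes any effect that reverses after stopping; an on-treatment version should be added

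*SAP*

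**What the plan says.** - **Summary.** SAP 16.3 specifies "Observed and change/percent change from baseline by analysis visit for hematology and blood chemistry measurements". It also summarizes creatinine and eGFR by baseline eGFR category.
- **Population.** SAP 16: "The Safety Analysis Set (SAS) will be used for all safety analyses". SAP 6.3 defines that set as "all patients in FAS who received at least 1 dose of double-blind IMP", grouped by the treatment actually received. Being on IMP when the sample is drawn is not required.
- **Visit assignment.** SAP 7.2.4: "study assessments will be assigned to analysis visits based on the Study Day (Section 7.2.2), and analysis visit windows specified in Appendix 3". The date of last dose plays no part, and Appendix 3 runs to Month 66 (Day 2098).
- **Sampling after stopping.** Protocol 6.3 follows patients to study termination "irrespective of whether the patient is continuing to receive study treatment". If a patient who has stopped IMP agrees to clinic visits, Protocol 10.6 says that "the visit will include all procedures and assessments except for those pertaining to IMP management". Protocol 10.7.3 also allows telephone or less frequent contact, so not every such patient gives samples.
- **On-treatment version elsewhere.** SAP 15.4.2 adds on-treatment summaries for lipids, hs-CRP, HbA1c and fasting glucose, in which "values measured more than 7 days after the Date of Last Dose of IMP will be excluded". It names no liver, renal, muscle or hematology parameter.
- **Reversibility.** Protocol 4.2.2 names as target organs in repeat-dose toxicology the liver in rats and "liver and kidney in monkeys, and changes were reversible following cessation of treatment".

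**The concern.** A by-visit mean is normally read as a picture of the drug effect over time. Here the active-group mean at a late visit averages patients still taking bempedoic acid with patients who may have stopped years before. If the effect fades off drug, the group mean drifts toward placebo as stopping accumulates. A reader could not tell a waning effect from a growing share of untreated patients. Long-term safety is a stated secondary objective, and the latest visits are where the mixing is greatest. For a harm signal, the error runs toward reassurance.

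The data to separate the two explanations will exist, since the last-dose date is already derived (DLDOSE, SAP 7.2.1). The plan uses it for biomarkers that serve efficacy, but not for the rest of the laboratory panel.

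**Working it through.** The plan states no figure on this point, so there is none to reproduce.

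**Formula.** Suppose the effect is zero on placebo, returns to zero off drug, and stopping is unrelated to the laboratory value. Then

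expected by-visit difference = (1 − f) × on-drug effect,

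where f is the off-IMP share of active-group samples in the window. With annual stopping hazard h, time t in years, and r the share of stopped patients who still give clinic samples,

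d = 1 − exp(−h·t), and f = d·r / (1 − d + d·r).

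**Inputs.** The documents give neither h nor r. I assume h = 5, 10 and 15% per year, and r = 1, 0.5 and 0.25.

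**Example.** For h = 10% at Month 42 (t = 3.5), d = 1 − exp(−0.35) = 0.295. With r = 1, f = 0.295 and 70.5% of the effect remains. With r = 0.25, f = 0.074 / (0.705 + 0.074) = 0.095 and 90.5% remains.

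**Percentage of a fully reversible effect left in the by-visit difference (h = 5 / 10 / 15%)**

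| Visit | r = 1 | r = 0.5 | r = 0.25 |
|---|---|---|---|
| Month 6 | 97.5 / 95.1 / 92.8 | 98.8 / 97.5 / 96.3 | 99.4 / 98.7 / 98.1 |
| Month 12 | 95.1 / 90.5 / 86.1 | 97.5 / 95.0 / 92.5 | 98.7 / 97.4 / 96.1 |
| Month 24 | 90.5 / 81.9 / 74.1 | 95.0 / 90.0 / 85.1 | 97.4 / 94.8 / 92.0 |
| Month 42 | 83.9 / 70.5 / 59.2 | 91.3 / 82.7 / 74.3 | 95.4 / 90.5 / 85.3 |
| Month 60 | 77.9 / 60.7 / 47.2 | 87.6 / 75.5 / 64.2 | 93.4 / 86.0 / 78.2 |

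**Simulation of the fix and of worst-value outputs.** This used 200,000 patients per arm, r = 1, an on-drug shift of 0.30 SD that vanishes off drug, and eight visits to Month 42.

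| Output (h = 5 / 10 / 15%) | All values | On treatment only |
|---|---|---|
| Month 42 mean difference (SD) | 0.246 / 0.207 / 0.179 | 0.295 / 0.295 / 0.301 |
| Active group, worst value above 2.5 SD (%) | 7.2 / 7.1 / 6.8 | 6.9 / 6.6 / 6.1 |
| Risk ratio for that threshold | 1.92 / 1.92 / 1.82 | 2.02 / 2.10 / 2.08 |

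The mean loses up to about 40% of the effect (0.179 / 0.30 = 0.60), and the on-treatment version recovers it. The worst-value comparison moves much less, because a later off-drug value cannot erase an earlier on-drug extreme.

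**Which parameters are exposed.** SAP Table 2 gives worst-value shifts for fasting glucose, HbA1c, ALT, AST, eGFR and uric acid. Fasting glucose and HbA1c also have the on-treatment summary. Creatinine, BUN, CK, total bilirubin and hemoglobin have no Table 2 shift. Bilirubin does appear in the liver scatterplot.

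**The case against.** Several objections are sound, and they limit the point.

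- **Other outputs keep on-drug extremes.** Besides the Table 2 shifts and the plot of peak ALT or AST against bilirubin, Appendix 10 flags changes in creatinine, BUN, CK, bilirubin, eGFR and hemoglobin. SAP 16.3 then lists every value of a flagged patient, so recovery can be followed in those individuals. A reader might infer that laboratory safety as a whole is diluted; the documents do not support that. However, listings do not compare groups, and worst values do not show a modest mean shift over time.
- **Reversibility is not established in patients.** Protocol 4.2.2 reports target-organ findings in animals. Its sentence on laboratory changes does not mention reversal, and uric acid, CK and hemoglobin are not covered. Protocol 12.1.6.3.1 and 12.1.6.3.2 contemplate liver tests and CPK returning to baseline before rechallenge. That is consistent with reversal but does not demonstrate it.
- **The all-values view is legitimate.** It matches the adverse-event window in SAP 16.1.1, which runs to study end. On-treatment means have their own bias: IMP may be stopped for ALT/AST or CK, so they lose affected patients and could themselves understate harm. Neither view replaces the other.
- **SAP 15.4.2 is an efficacy sensitivity section.** It sets no rule that SAP 16.3 breaks, so the contrast is a gap in coverage and not a contradiction.
- **The tables are descriptive.** SAP 16 plans no between-group testing of safety data unless specified, so no formal error rate is affected.

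Appendix 7 and the body of Table 3 are not in the available text. Both concern abnormality criteria, not by-visit means, but a further rule there cannot be excluded.

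**Conclusion.** The point holds for the by-visit summaries in SAP 16.3. They include values taken any time after IMP was stopped, so an effect that reverses off drug is diluted in the later means. The direction follows from the documents for any reversible effect.

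The size does not. It rests on assumed stopping of 5 to 15% per year, assumed clinic attendance after stopping, and complete reversal. On those assumptions the loss is small through Month 12. At Month 42 it ranges from about 5% (5% stopping, a quarter sampled) to about 41% (15% stopping, all sampled). Partial reversal would give less.

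A reader might infer that the plan hides a known human liver or renal effect, or that treated and untreated values are pooled under the randomized arm. Neither is supported: the evidence of reversal is from animals, and the Safety Analysis Set groups by treatment received. This is a worthwhile, inexpensive improvement to interpretability. The primary efficacy analysis is untouched.

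**What to change.** In SAP 16.3, keep the all-values tables and make these additions in the Safety Analysis Set:

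1. By-visit summaries of creatinine, eGFR, BUN, uric acid, ALT, AST, total bilirubin, CK and hemoglobin, leaving out values more than 7 days after DLDOSE, as SAP 15.4.2 already does for the biomarkers.
2. The number of patients on and off IMP among those contributing a value at each visit. This shows the actual f and makes the all-values tables readable.
3. For patients who stop early, one table of the last on-treatment value against the first value more than 30 days after DLDOSE.
4. A note that on-treatment means condition on staying on drug, and that a last-dose filter does not remove temporary interruptions, for which Protocol 10.7.2 sets no time limit.

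The cost is a date filter on existing table programs, one count per visit and one extra table. No new data are needed, and no dosing or stopping rule changes.
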